## Effect of a Digital Engagement Strategy on Healthcare Worker Mental Health and Well-being: A Randomized Controlled Trial

Initiative, FOCUS on health and leadership for women, Penn Promotes research on sex and gender in health, and the Program for Health Equity in Education and Research. Furthermore, we will recruit in-person across the Penn Medicine campus such as tabling outside of prominent buildings and departments (New Pavilion and cafeterias) and attend department morning huddles / meetings to accommodate staff members who have limited access to their email accounts. We will also be intentional about diversity of representation in the images in all study materials and highlight the diversity in our project team. We base our power considerations on baseline data presented in an RCT conducted by Graham et al. In their study, they report a mean baseline PHQ-9 of 14.0 (SE=5.0) and mean GAD-7 of 11.6 (SE=4.6). We assume a type I error rate of 2.5% (.05/2) to account for the two separate outcomes that we will be evaluating. We aim to enroll 1250 participants with the anticipation that there will be 20% attrition.

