## Effect of a Digital Engagement Strategy on Healthcare Worker Mental Health and Well-being: A Randomized Controlled Trial

through the last observation. A  $p < 0.05$  will be deemed statistically significant but emphasis will be placed on point estimates and confidence intervals. Secondary outcomes of mental healthcare utilization, satisfaction with connection to services, and qualitative feedback on mobile engagement will also be modeled using GEE with mean models specified based on the distribution of the specific outcome (e.g. Poisson or negative binomial for number of mental healthcare visits, logit for binary responses).

Potential associations between system-level or regional level case burden and PHQ-9 and GAD-7 scores at baseline and over-time will be assessed with generalized linear models and GEE. Exploratory Aim 1: Statistical approach: The statistical approach for studying HTE will be to test for the statistical interaction between the intervention and race and separately by gender in the GEE models described above. Although our study was not designed specifically to detect HTE, if 20% of our trial participants are Black (based on targeted recruitment efforts), our study will achieve 80% power (assuming type I error of 0.05) to detect a 1.8 difference in mean GAD-7 scores and a 2.0 difference in mean PHQ-9 scores between arms at 6 months. We anticipate that at least 50% of participants will be female. Hence, our study is powered to detect a 1.2 difference in mean GAD-7 scores and a 1.3 difference in mean PHQ-9 scores between arms at 6 months among women.

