### 4. Primary Outcome Variable

Measures were selected based on clinical relevance, validity in the HCW population, and meaningfulness to the target population. To facilitate data sharing, measures below were also identified to align with the NIMH data archive when possible. The primary outcome will be depression and anxiety as measured by the Patient Health Questionnaire (PHQ-9) and General Anxiety Disorder (GAD-7) respectively. PHQ-9 and GAD-7 have been validated and used in multiple studies and provide easy, simple scales to quickly assess for depression and anxiety. PHQ9 is a 9-item score which ranges from 0 (least depressed) to 27 (most depressed). GAD-7 is a 7-item scale which assess the frequency of anxiety symptoms over the past two weeks on a 4-point Likert-scale ranging from 0 (never) to 3 (nearly every day). The total score of GAD-7 ranged from 0 to 21, with increasing scores indicating more severe functional impairments as a result of anxiety.

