#### 7.2 Subjects at Penn 1,275

#### 7.3 Accrual

To recruit potential study participants, we will send an email about the study to the entire Penn Medicine employee listserv, as these individuals are the same recipients of Penn Medicine news and Covid-19 updates who have received prior information about the availability of Cobalt. Emails will be sent up to 5 times to this employee list. The plan to outreach to employees in this manner has been approved by both Penn Medicine Human Resources and the Penn Medicine Chief Operation Officer. We will specifically engage recruitment champions in the study design and for support in extending the reach of the recruitment email to underrepresented minority HCWs. These recruitment champions will include each Departments Vice Chair for Diversity and Inclusion to support sending the email about the study to their Departments and groups within their Departments specifically focused on diversity and inclusion. We will also engage Centers, Departments, and Groups at Penn Medicine to support dissemination of the study announcement. These include the Office of Inclusion and Diversity, the Alliance of Minority Physicians, Penn Medicine Center for Health Equity Advancement, Bold Solutions Initiative, FOCUS on health and leadership for women, Penn Promotes research on sex and gender in health, and the Program for Health Equity in Education and Research. Furthermore, we will recruit in-person across the Penn Medicine campus such as tabling outside of prominent buildings and departments (New Pavilion and cafeterias) and attend department morning huddles / meetings to accommodate staff members who have limited access to their email accounts. We will also be intentional about diversity of representation in the images in all study materials and highlight the diversity in our project team. We base our power considerations on baseline data presented in an RCT conducted by Graham et al. In their study, they report a mean baseline PHQ-9 of 14.0 (SE=5.0) and mean GAD-7 of 11.6 (SE=4.6). We assume a type I error rate of 2.5% (.05/2) to account for the two

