## Effect of a Digital Engagement Strategy on Healthcare Worker Mental Health and Well-being: A Randomized Controlled Trial

separate outcomes that we will be evaluating. We aim to enroll 1275 participants with the anticipation that there will be 27.5% attrition.

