
### **9. Analysis Plan**

We will conduct an intent to treat (ITT) analysis. The ITT analysis will include all randomized participants in the groups to which they were randomly assigned. Baseline demographic and clinical characteristics will be reported as frequency and percent for categorical variables and median and distribution for continuous variables. We will compare baseline characteristics between intervention and control arms using t-tests for continuous variables and chi-squared tests for categorical variables. The goal of these comparisons will be to determine if the two arms are balanced on baseline variables after randomization. Our primary analysis will focus on the difference in PHQ-9 and GAD-7 scores at 6 months between the two arms. We will estimate and test differences in means between arms using two- sample

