## Effect of a Digital Engagement Strategy on Healthcare Worker Mental Health and Well-being: A Randomized Controlled Trial

t-tests and generalized linear models that account for baseline measurements of PHQ-9 and GAD-7. Missing data will be assessed for patterns and multiple imputation will be used if deemed appropriate. Baseline covariates that are found to be imbalanced between arms may be adjusted for in the model if they were deemed to be potential confounders a priori to adjust for potential confounding and for efficiency gain. We will use all available PHQ-9 and GAD-7 scores on eligible patients from randomization through the last observation. A p<0.05 will be deemed statistically significant but emphasis will be placed on point estimates and confidence intervals. Secondary outcomes of mental healthcare utilization, satisfaction with connection to services, and qualitative feedback on mobile engagement will also be modeled using GEE with mean models specified based on the distribution of the specific outcome (e.g. Poisson or negative binomial for number of mental healthcare visits, logit for binary responses). Potential associations between system-level or regional level case burden and PHQ-9 and GAD-7 scores at baseline and over-time will be assessed with generalized linear models and GEE. Exploratory Aim 1: Statistical approach: The statistical approach for studying HTE will be to test for the statistical interaction between the intervention and race and separately by gender in the GEE models described above. Although our study was not designed specifically to detect HTE, if 20% of our trial participants are Black (based on targeted recruitment efforts), our study will achieve 80% power (assuming type I error of 0.05) to detect a 1.8 difference in mean GAD-7 scores and a 2.0 difference in mean PHQ-9 scores between arms at 6 months. We anticipate that at least 50% of participants will be female. Hence, our study is powered to detect a 1.2 difference in mean GAD-7 scores and a 1.3 difference in mean PHQ-9 scores between arms at 6 months among women. Aim 2: Power: no power calculation will be performed for this qualitative aim consistent with prior qualitative aims we will aim to interview 80 participants from Aim 1 and evaluate themes until saturation Analysis: Using thematic analysis, we will analyze HCW interview transcripts to identify recurring themes in attitudes and beliefs toward mental health, well-being, and mental health care or resources. Interview audio will be transcribed and uploaded into Nvivo software (available as a Penn resource). In total we plan for up to 80 semi-structured interviews, or until inductive thematic saturation is reached in each group meaning no new themes are emerging. Analysis of qualitative, semi-structured interviews utilizes a series of systematic steps in transcribing, developing a code for thematic content, and subsequent coding of interviews. A modified grounded theory approach will be used to evaluate interview transcriptions. Analysis will begin shortly after the first few interviews are completed. An emergent, iterative open coding process will be followed and two trained coders from the research team will jointly read five transcripts and draft the outline of a codebook. Each coder will then independently code five more transcripts and adjust the codebook as needed. We will review the codes, resolve discrepancies and finalize coding procedures. Following adjudication of any areas of discrepancy, the research team coders will be assigned batches of transcripts for independent coding, sharing 25% of the transcripts in each batch for ongoing inter-rater agreement assessment. We will review coding for interrater reliability, measured by Cohens kappa (0.8), and overall comprehensiveness. If a high kappa is not achieved, further double coding and refining of the code will continue. This approach to coding and analyzing qualitative data has been widely used. Strategies used to ensure reliability and validity in the qualitative data will include a comprehensive audit trail, checks between coders, team debriefing, and corroboration of findings across participants.

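### Section 7.3 plans each of the two primary outcomes at a 2.5% type I error, but Section 9 calls any p<0.05 significant, so the primary tests lack the error control the trial was planned with

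*Combined protocol and SAP*

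**What the plan says.** Final protocol, Section 4 (Primary Outcome Variable), makes depression and anxiety primary, each on its own scale: "The primary outcome will be depression and anxiety as measured by the Patient Health Questionnaire (PHQ-9" for depression, and GAD-7 for anxiety.

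Section 7.3 (Accrual) gives the planning error rate: "We assume a type I error rate of 2.5% (.05/2) to account for the two" "separate outcomes that we will be evaluating".

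Section 9 (Analysis Plan) identifies the primary comparison: "Our primary analysis will focus on the difference in PHQ-9 and GAD-7 scores at 6 months between the two arms". For the test it lists two-sample "t-tests and generalized linear models that account for baseline measurements of PHQ-9 and GAD-7" and does not rank them. Before it turns to secondary outcomes it gives its only significance rule: "A p<0.05 will be deemed statistically significant but emphasis will be placed on point estimates and confidence intervals". It names no confidence level.

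The earlier protocol in the same file has the same pair of statements. Its Section 6.3 says "We assume a type I error rate of 2.5% (.05/2) to account for the two separate outcomes that we will be evaluating", and its Section 8 applies the same p<0.05 rule, which "will be deemed statistically significant but emphasis will be placed on point estimates and confidence intervals". The final version changed enrolment and attrition but left this mismatch in place.

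**The concern.** The reason given for the 2.5% is that two outcomes are evaluated. That reason makes sense only if each is then tested at 2.5%. Section 9 does not carry the split forward. Its threshold follows directly on the primary-analysis text, so it cannot reasonably be read as covering secondary outcomes only.

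Two analysts following the plan could disagree on any primary result with p from 0.025 up to 0.05. One would apply Section 9 and declare significance; the other would apply the Section 7.3 level and not. With the rule open, the choice could be made after the results are known. If either scale can support a claim, testing both at 0.05 takes the family-wise error over the two primary comparisons above 5%.

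The unranked pair of analyses adds to this. If either the t-test or the adjusted model may count for a scale, there are four chances of a primary claim rather than two.

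**Working it through.** **Inputs from the documents.** Per-outcome planning error 2.5% (Section 7.3); decision threshold 0.05 (Section 9); 1275 enrolled with 27.5% attrition (Section 7.3); spread 5.0 for PHQ-9 and 4.6 for GAD-7 (Section 7.3, printed as SE).

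**Assumptions.** Two-sided tests; 1:1 allocation; success on either outcome; the printed SE values read as SDs; 80% power for the main comparison (stated only for a subgroup); correlation between the two test statistics from 0 to 0.9.

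**1. The plan's own figure.** 0.05/2 = 0.025, as stated. The critical |z| is 2.241 at 0.025 and 1.960 at 0.05.

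**2. Check on reading SE as SD.** The plan gives no detectable difference for the main comparison, but Section 9 gives subgroup figures. Use (1.960 + 0.8416) × SD × √(2/n per arm) with the earlier protocol's 1250 × 0.80 = 1000 completers:
- Black participants (20%, 100 per arm): 1.98 for PHQ-9 and 1.82 for GAD-7, against 2.0 and 1.8 stated.
- Women (50%, 250 per arm): 1.25 and 1.15, against 1.3 and 1.2 stated.

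So the SD reading and 1:1 allocation reproduce the plan's figures, and those subgroup figures use 0.05.

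**3. Family-wise error.** FWER = 1 − P(|Z1| < c, |Z2| < c), bivariate normal. With independence this is 1 − 0.95² = 0.0975 at 0.05 each and 1 − 0.975² = 0.0494 at 0.025 each.

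| Correlation | p<0.05 each | p<0.025 each |
|---|---|---|
| 0 | 9.75% | 4.9% |
| 0.5 | 9.1% | 4.7% |
| 0.7 | 8.4% | 4.3% |
| 0.8 | 7.8% | 4.0% |
| 0.9 | 7.0% | 3.6% |

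**4. Where the two levels disagree.** 1275 × 0.725 = 924 completers, 462 per arm; √(2/462) = 0.0658. The observed difference at the threshold is c × SD × 0.0658 (unadjusted t-test):
- GAD-7: 1.960 × 4.6 × 0.0658 = 0.593 and 2.241 × 4.6 × 0.0658 = 0.678.
- PHQ-9: 1.960 × 5.0 × 0.0658 = 0.645 and 2.241 × 5.0 × 0.0658 = 0.737.

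**5. Price of the stricter level.** Detectable difference = (c + 0.8416) × SD × 0.0658, again unadjusted:
- GAD-7: 0.93 at 0.025, against 0.85 at 0.05.
- PHQ-9: 1.01 at 0.025, against 0.92 at 0.05.

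Baseline adjustment multiplies the figures in steps 4 and 5 by √(1 − r²), where r is the correlation of baseline with 6-month score. For an assumed r of 0.6 that is √(1 − 0.36) = 0.8. The windows become about 0.47–0.54 (GAD-7) and 0.52–0.59 (PHQ-9), and the detectable differences at 0.025 become 0.75 and 0.81.

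**6. Two unranked tests per outcome.** In a simulation where either the t-test or the adjusted model could count at 0.025 for either scale, the family-wise error was 6.4% at between-outcome correlation 0.8 and baseline correlation 0.6. It ran from 5.4% to 8.3% over between-outcome correlations of 0–0.9 and baseline correlations of 0.5–0.7. All these correlations are assumed. Correcting the threshold alone would therefore not secure 5%.

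**The case against.** The strongest reply is that Section 7.3 is a planning section. It assumes 2.5% for power and issues no verdict, so Section 9 holds the only decision rule. That describes the text correctly, but it does not help: the trial would then be planned with one error control and judged with another.

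A second reply is that 0.05 in Section 9 is the overall level, with the division already given in Section 7.3. The .05/2 notation makes this plausible. Section 9 does not say it, though, and a reader applying the sentence literally would test each scale at 0.05.

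Third, if both scales had to succeed, the error would be at most 5% with each tested at 0.05. That is right, and the inflation depends on an either-outcome rule that no section states. But a both-must-succeed rule would make the .05/2 split pointless, so the split points to either.

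Fourth, Section 9 puts its emphasis on estimates and intervals. This softens the threshold without removing it, and since no confidence level is given, the intervals are ambiguous in the same way.

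Two points of scale stand. The zone of disagreement is narrow, about 0.09 points on either scale. And the upper end of the error range needs near-independence between two scales answered by the same people.

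**Conclusion.** The concern holds. Followed literally, Section 9 does not deliver the error control on which Section 7.3 bases its planning, and it leaves the verdict open for primary p-values from 0.025 up to 0.05. Under two-sided testing with success on either scale, the family-wise error over the two primary comparisons is about 7–10%, against 3.6–4.9% at the planned level. It exceeds 5% even at an assumed correlation of 0.9. Secondary, case-burden and subgroup tests are outside this figure. The point-scale figures also rest on 1:1 allocation and on spread values taken from a cited trial's baseline, and they apply to the unadjusted test. The mismatch itself rests on none of these assumptions. Because it concerns the decision rule for the trial's main claim, it must be corrected before unblinding.

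**What to change.** Insert in Section 9:

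> PHQ-9 at 6 months and GAD-7 at 6 months are each tested at two-sided p<0.025 and reported with 97.5% confidence intervals; a claim may rest on either. For each scale the single decisive test is the arm effect in the generalized linear model adjusted for that scale's baseline score. The t-test and any model with further covariates are supportive. The 0.05 threshold applies only to secondary and exploratory analyses.

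If Holm's procedure is preferred, test the smaller p-value against 0.025 and, only if that is significant, the other against 0.05. Keep the 97.5% intervals and note that they are more conservative than the Holm test. If the sponsor intends that both scales must succeed, say so and drop the split from Section 7.3.

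The cost is a few sentences. The sample size does not change, because 0.025 is already the planning level. Against testing at 0.05, the unadjusted detectable difference rises by about 0.08 points on GAD-7 (0.93 − 0.85) and 0.09 on PHQ-9 (1.01 − 0.92). Section 9 also leaves multiple imputation to later judgement. The wording above does not settle that, so how missing scores enter the decisive test should be fixed in the same edit.

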
## Effect of a Digital Engagement Strategy on Healthcare Worker Mental Health and Well-being: A Randomized Controlled Trial

survivors were more likely to be older (median age 62), male (38% vs. 22%), Asian (20% vs. 9%), or Black (32% versus 25%). The increased exposure to COVID-19 may also limit physical contact of HCW with usual support networks and systems (e.g. family or faith-based groups) or lead to increased stress because of home based caregiving for elderly or immunocompromised family members. HCWs identifying as Black, indigenous, or of color are a vulnerable population. Prior reports support that black adults are approximately 10% more likely to report psychological distress when compared with white adults. Data from the Health and Human Services Office of Minority Health also shows that black adults are more likely than white adults to report hopelessness, sadness, and feeling like everything is an effort. There are significant barriers to accessing mental health care for black adults and it is estimated that only one in three black adults who need mental health care receive it. Many reasons contribute to these disparities including: costs of care, stigma associated with care, provider bias, lack of knowledge regarding available mental health therapies, and the lack of minority mental health professionals. For those who do receive care, the care is often of lower quality and not culturally aligned. Black HCWs have historically been subject to racism, discrimination, and inequity--and the national events centered around racial injustice coupled with COVID-19 have likely exacerbated mental health and well-being in measurable and sustained ways. Minority HCWs were already strained, often working within settings where they themselves are subject to microaggressions, overt acts of racism, structural racism and are direct observers of racial inequities in patient care leading to significant disparities in morbidity and mortality. Racial minorities are also disproportionately in jobs with high exposure risk including grocery stores, public transportation, factories, and health care facilities. A meta-analysis of 293 studies identified that racism significantly contributed to worse mental and physical health. Based on findings from more than 60 structured interviews with Black HCWs, the noted sociologist Adia Wingfield summarized her findings and noted: being a Black health care worker comes with specific difficulties that can easily go unnoticed. In a pandemic where Black populations are among the hardest hit, these difficulties are likely being magnified exponentially. Health care systems are undoubtedly taxed, but in the interest of their workers, they should consider ways they can support Black health care providers to offset the kinds of burnout and stresses research indicates they are likely experiencing right now. In this national emergency, health care systems may need to think past providing health care just for patients and consider the health of their workers, perhaps through counseling and support groups, heeding employees suggestions for how systems can be improved. The social and economic consequences of COVID-19 are predicted to affect women differently than men. Prior reports support that women have been more likely to lose their jobs or leave them during the pandemic due to a need to provide child and elder care as well as to support home schooling. While this unpaid labor has increased, paid work opportunities have also decreased for women. Increases in sexual and physical violence toward women during lockdowns have also been reported. The United Nations has identified increased vulnerability of female frontline workers and the need for targeted programs to specifically address their unique mental health needs due to a multitude of stressors. Prior reports have also focused on female frontline providers and physician researchers and threats to their professional careers, particularly academic, advancement due to barriers in work productivity as a result of COVID-19. The psychological impact of the delay in academic career progression (e.g. fewer grant submissions, fewer peer-reviewed publications, fewer leadership opportunities) could be pronounced and long standing. Considering how the pandemic has led to considerable strain on women and the unique impact on women in health care, this proposal specifically focuses on evaluating if Cobalt+ will have a greater impact on women and can serve as a platform for addressing inequities in mental health care for this vulnerable population. COVID-19 has increased the use and application of digital technologies in health care including text messaging, mobile surveys, and telemedicine. Evolving and rapidly adopted approaches in mobile engagement through digital technology create scalable opportunities to assess individuals needs in real-time and can be used to rapidly deploy tailored well-being and mental health interventions. This

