
## Effect of a Digital Engagement Strategy on Healthcare Worker Mental Health and Well-being: A Randomized Controlled Trial

from those in the intervention arm Cobalt+ (n=up to 40). Using data from Aim 1, we will use a deviance sampling approach to identify HCW from the top and bottom 25% percentiles of anxiety and depression scales from month 6 to baseline. This deviant selection is intentional to maximize the potential to identify themes unique to high or low levels of mental health strain. Individual scale scoring will not be revealed in order to limit responder bias, increase response rates and avoid attribution bias. We intend Aim 2 study sample to be similar to the Aim 1 gender and race breakdown. Since we oversampled Black participants in Aim 1, we intend to have at least 25% Black participants in Aim 2. We will recruit HCWs using a series of e-mails (up to 4 email invitations) and text messages (up to 3 text invitations). We will contact participants to obtain consent, ensure study procedures are described, answer questions and offer a \$50 gift card for their time. The goal is to conduct up to 80 audio-recorded semi-structured interviews (~20-30 minutes). Interview questions will be aligned with themes from our preliminary studies and focus groups with front line healthcare workers early in the pandemic. Participants will be contacted one month following the end of the Aim 1 study period and consented via WTH. Participants will not be informed as to why they were selected and confidentiality will be maintained. There is variability in how individuals experience anxiety, depression, stress and overall well-being.

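### Exploratory Aim 1: the power figures for Black participants were not recalculated when expected completers fell from 1,000 to 924, and no figure is given for the planned interaction tests

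*Combined protocol and SAP*

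**What the plan says.** The final protocol, Section 9 (Analysis Plan, Exploratory Aim 1), says that heterogeneity of treatment effect (HTE) will be studied as follows: "test for the statistical interaction between the intervention and race and separately by gender in the GEE models described above". The power statement comes next. It opens with a caveat and a condition, "Although our study was not designed specifically to detect HTE, if 20% of our trial participants are Black", and continues "our study will achieve 80% power (assuming type I error of 0.05) to detect a 1.8 difference in mean GAD-7 scores", with 2.0 as the matching PHQ-9 figure. Both are described as differences between arms at 6 months. For women, expected to be at least half of participants, the figures are 1.2 (GAD-7) and 1.3 (PHQ-9).

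The initial protocol, Section 8, gives the same four figures. The sample-size statements differ:

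- Initial protocol, Section 6.3: "We aim to enroll 1250 participants with the anticipation that there will be 20% attrition".
- Final protocol, Section 7.3: "We aim to enroll 1275 participants with the anticipation that there will be 27.5% attrition".

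Both accrual sections take their spread from an earlier trial's baseline data: 4.6 for GAD-7 and 5.0 for PHQ-9, each labelled SE.

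**The concern.** There are two separate points.

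1. Enrolment and attrition were both revised, but the power sentences were not. If the race pair was calculated on the earlier number of completers, the 80% it claims no longer follows from the current design.
2. The planned analysis asks whether the treatment effect differs between subgroups. The printed figures answer another question: how large an arm difference can be detected inside one subgroup. An interaction estimate has a larger standard error, so its detectable size is larger.

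The second point bears on a stated interest of the trial. The Background says "this proposal specifically focuses on evaluating if Cobalt+ will have a greater impact on women", which is an interaction question, and the plan gives no detectable size for it. A reader who sees 80% power directly after the interaction test could take a non-significant interaction as better evidence of a uniform effect than it is.

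**Working it through.** **Inputs**
- SD: 4.6 (GAD-7) and 5.0 (PHQ-9), from Section 7.3. They are printed as SE but read here as SDs, because the plan's figures reproduce only that way.
- Two-sided alpha 0.05 (the plan does not state sidedness) and 80% power, so k = 1.960 + 0.842 = 2.802.
- 1:1 allocation (assumed) and no gain from baseline adjustment.
- Subgroup share f: 0.20 Black and 0.50 female, from Section 9.
- Completers N (derived; neither number is printed): 1250 × 0.80 = 1,000 in the initial protocol and 1275 × 0.725 = 924.4 in the final one.

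**Formulas**
- Within a subgroup: SE = SD × √(4/(N f)).
- Interaction (subgroup against all others): SE = SD × √(4/(N f) + 4/(N(1 − f))).
- Detectable difference = k × SE. Power at a difference d = Φ(d/SE − 1.960).

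**Step 1: reproduce the printed figures at N = 1,000**
- Black, 200 completers: 2.802 × 4.6 × √(4/200) = 1.82; with SD 5.0, 1.98. Printed: 1.8 and 2.0.
- Women, 500 completers: 2.802 × 4.6 × √(4/500) = 1.15; with SD 5.0, 1.25. Printed: 1.2 and 1.3.

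All four agree after rounding.

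**Step 2: repeat at N = 924.4**

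| Subgroup | Completers | SE (GAD-7 / PHQ-9) | Detectable | Power at printed values |
|---|---|---|---|---|
| Black, 20% | 184.9 | 0.677 / 0.735 | 1.90 / 2.06 | 75.8% / 77.6% |
| Women, 50% | 462.2 | 0.428 / 0.465 | 1.20 / 1.30 | 80.1% / 79.8% |

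To one decimal the race pair becomes 1.9 and 2.1. The women's pair is unchanged.

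The Black completers needed for 80% power number 4 × (2.802 × 4.6/1.8)² = 205 for a GAD-7 difference of 1.8, and 4 × (2.802 × 5.0/2.0)² = 196 for a PHQ-9 difference of 2.0. These are 22.2% and 21.2% of 924.

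**Step 3: the planned interaction tests at N = 924.4**

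| Interaction | SE (GAD-7 / PHQ-9) | Detectable | Power if the interaction equals the printed figure | 95% CI half-width |
|---|---|---|---|---|
| Race, 20% Black | 0.757 / 0.822 | 2.12 / 2.30 | 66.3% / 68.2% | 1.48 / 1.61 |
| Gender, 50% female | 0.605 / 0.658 | 1.70 / 1.84 | 50.9% / 50.7% | 1.19 / 1.29 |

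**Step 4: sensitivity**

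A baseline correlation r multiplies each SE by √(1 − r²). The plan gives no r, so these values are assumptions.
- Within Black participants, r = 0.3 gives 79.6% and 81.3% at the printed values.
- Race interaction: 70.3% and 72.2% at r = 0.3; 78.5% and 80.2% at r = 0.5.
- Gender interaction: 54.7% and 54.4% at r = 0.3; 62.9% and 62.6% at r = 0.5.
- At an assumed 75% female and r = 0, the detectable gender interaction rises to 1.96 and 2.13, and power at 1.2 and 1.3 falls to about 40%.

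**Step 5: could the race pair already be interaction figures?**

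On all 1250 enrolled with no attrition, the detectable race interaction is 1.82 and 1.98, which also rounds to the printed pair. But the text describes differences between arms and plans for attrition, and the same method gives 1.46 and 1.59 for gender, not 1.2 and 1.3. Within-subgroup differences on 1,000 completers are the reading that fits all four figures.

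**The case against.** The strongest case against is that the shortfall is small and may not arise in practice.

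- **Size.** The gap is 0.10 GAD-7 and 0.06 PHQ-9 points. At 1,000 completers the printed 1.8 already gave 79.0%, so the revision cost only about 3 points of power (79.0% to 75.8% for GAD-7, 80.7% to 77.6% for PHQ-9). This stands and limits the weight of the point.
- **Baseline adjustment.** The planned models account for baseline scores. A correlation of about 0.31 (GAD-7) or 0.24 (PHQ-9) would restore 80%. That is plausible, but no correlation is stated, and the printed figures reproduce without any adjustment.
- **Timing of attrition.** The 27.5% has no time point, and follow-up runs to month 9. If month-6 attrition were 20% of 1275, power would be 79.8% and 81.5%. The plan states no separate month-6 rate, and its own figures were built with full attrition applied. Multiple imputation is only conditional, and the plan does not show that it would recover the lost information.
- **Black share.** Section 6.2 says "Since we oversampled Black participants in Aim 1, we intend to have at least 25% Black participants in Aim 2". At a 25% share, power at the printed values is 84.5% and 86.0%. However, 25% is an Aim 2 target, and the power sentence is conditional on 20%.
- **Disclosure.** The plan says it was not designed to detect HTE, labels the aim exploratory, describes differences between arms, and marks the second pair as applying to women. It claims no power for an interaction. This is fair: adding detectable interactions is an improvement to the text, not the correction of a false claim.

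**Conclusion.** The concern holds and is minor. On the plan's own inputs, the 80% power stated for differences of 1.8 and 2.0 among Black participants belongs to the initial protocol's 1,000 completers. At the final protocol's 924 it is 76% and 78%, and the differences detectable with 80% power are 1.9 and 2.1. The women's figures are correct as printed.

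None of the four figures refers to the planned interaction tests, and the race pair does not say that it applies within the subgroup. For those tests the detectable sizes are about 2.1 and 2.3 (race) and 1.7 and 1.8 (gender at 50% female).

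These results assume 1:1 allocation, a two-sided 5% test, the printed SEs read as SDs, the full 27.5% attrition at month 6 and equal across subgroups, and no baseline adjustment. A modest baseline correlation, or a Black share of about 22%, would remove the shortfall in the race pair. Neither changes the finding that the gender interaction test has well under 80% power at the printed differences: about 51% unadjusted and 63% at r = 0.5. The practical effect is limited, because the aim is exploratory and the plan already puts the emphasis on estimates and confidence intervals.

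**What to change.** In Section 9, Exploratory Aim 1, of the final protocol:

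1. Replace the Black-participant figures with about 1.9 (GAD-7) and 2.1 (PHQ-9), at 924 completers and a 20% share. Alternatively, keep 1.8 and 2.0 and state the share, baseline correlation or month-6 attrition under which they hold. This is the correction that is needed.
2. Keep 1.2 and 1.3 for women, and label all four figures as arm differences within the subgroup.
3. Add the detectable interactions with their assumptions: unadjusted, about 2.1 and 2.3 for race, and about 1.7 and 1.8 for gender at 50% female, larger if the female share is higher.
4. State that the interaction tests have less power than the within-subgroup figures suggest, and that HTE will be reported as interaction estimates with 95% confidence intervals. Expected half-widths are about 1.5 and 1.6 for race, and 1.2 and 1.3 for gender at 50% female.

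Items 2 to 4 are clarifications worth making in the same edit. The cost is wording and recalculated numbers only, with no extra participants and no change to any test. The one drawback is that the stated figures look slightly less favourable.
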